10.3. Abnormal Laboratory Values

An abnormal laboratory value is considered to be an AE if the abnormality:

- results in discontinuation from the study;
- requires treatment, modification/ interruption of fedratinib dose administration, or any other therapeutic intervention; or
- is judged to be of significant clinical importance, eg, one that indicates a new disease process and/or organ toxicity, or is an exacerbation or worsening of an existing condition.

Regardless of severity grade, only laboratory abnormalities that fulfill a seriousness criterion need to be documented as a serious adverse event.

If a laboratory abnormality is one component of a diagnosis or syndrome, then only the diagnosis or syndrome should be recorded as the AE. If the abnormality was not a part of a diagnosis or syndrome, then the laboratory abnormality should be recorded as the AE. If possible, the laboratory abnormality should be recorded as a medical term and not simply as an abnormal laboratory result (eg, record thrombocytopenia rather than decreased platelets).

10.4. Pregnancy

All pregnancies or suspected pregnancies occurring in either a female subject of childbearing potential or partner of childbearing potential of a male subject are immediately reportable events.

10.4.1. Females of Childbearing Potential

Pregnancies and suspected pregnancies (including elevated β -subunit of human chorionic gonadotropin [β -hCG] or positive pregnancy test in a female subject of childbearing potential

regardless of disease state) occurring while the subject is on fedratinib treatment, or within 30 days of the subject's last dose of fedratinib, are considered immediately reportable events. Investigational product is to be discontinued immediately and the subject instructed to return any unused portion of the fedratinib to the Investigator. The pregnancy, suspected pregnancy, or positive pregnancy test must be reported to Celgene Drug Safety immediately by email, phone or facsimile, or other appropriate method, using the Pregnancy Initial Report Form, or approved equivalent form.

The female subject may be referred to an obstetrician-gynecologist or another appropriate healthcare professional for further evaluation.

The Investigator will follow the female subject until completion of the pregnancy and must notify Celgene Drug Safety immediately about the outcome of the pregnancy (either normal or abnormal outcome) using the Pregnancy Follow-up Report Form, or approved equivalent form.

If the outcome of the pregnancy was abnormal (eg, spontaneous abortion), the Investigator should report the abnormal outcome as an AE. If the abnormal outcome meets any of the serious criteria, it must be reported as an SAE to Celgene Drug Safety within 24 hours of the Investigator's knowledge of the event.

All neonatal deaths that occur within 30 days of birth should be reported, without regard to causality, as an SAE. In addition, any infant death after 30 days that the Investigator suspects is related to the in-utero exposure to the fedratinib should also be reported as an SAE to Celgene Drug Safety within 24 hours of the Investigator's knowledge of the event.

10.4.2. Male Subjects

If a female partner of a male subject taking fedratinib becomes pregnant, the male subject taking fedratinib should notify the Investigator, and the pregnant female partner should be advised to call their healthcare provider immediately.

Males will be advised to use a latex condom during any sexual contact with FCBP prior to study entry and continue for 30 days following the last dose of fedratinib, even if he has undergone a successful vasectomy.

10.5. Reporting of Serious Adverse Events

Any AE that meets any serious criterion requires reporting as an SAE within 24 hours of the Investigator's knowledge of the event. This instruction pertains to initial SAE reports as well as any follow-up reports.

This requirement applies to all SAEs (regardless of relationship to IP) that occur during the study (from the time the subject signs informed consent until 30 days after the last dose of IP) or any SAE made known to the Investigator at any time thereafter that are suspected of being related to IP. Serious adverse events occurring prior to treatment (after signing the ICF) are to be recorded within the CRF, but do not require reporting to Celgene Drug Safety.

Where required by local legislation, the Investigator is responsible for informing the Institutional Review Board/Ethics Committee (IRB/EC) of the SAE and providing them with all relevant initial and follow-up information about the event. The Investigator must keep copies of all SAE source documents and all correspondence with the IRB/EC.

The SAE is recorded within the CRF, and the data is transmitted electronically to Celgene Drug Safety. In the event electronic transmission is not available, a paper SAE Report Form will be completed and sent directly to Celgene Drug Safety, ensuring the event is recorded on the CRF as well.

Queries pertaining to SAEs will be communicated from Celgene Drug Safety to the site via electronic data capture (EDC) or other appropriate method.

10.6. Expedited Reporting of Adverse Events

For the purpose of regulatory reporting, Celgene Drug Safety will determine the expectedness of events suspected of being related to fedratinib based on the Investigator Brochure.

In the United States, expedited reports sent to the FDA by the sponsor based on the reasonable possibility threshold are known as “IND safety reports” and will be reported in accordance with 21 CFR 312.32.

For reporting to the FDA, events that are not suspected to be causally related to fedratinib by the sponsor will not be considered adverse reactions. As per FDA regulations, events that are anticipated in the study population, listed in the IB, will not be considered adverse reactions on individual assessment and will be reviewed on an aggregate basis for assessment of frequency.

For countries within the European Economic Area (EEA), Celgene or its authorized representative will report in an expedited manner to Regulatory Authorities and Ethics Committees concerned, suspected unexpected serious adverse reactions (SUSARs) in accordance with Directive 2001/20/EC and the Detailed Guidance on collection, verification and presentation of adverse reaction reports arising from clinical trials on investigational products for human use (ENTR/CT3) and also in accordance with country-specific requirements.

Celgene or its authorized representative shall notify the Investigator of the following information

- Any AE suspected of being related to the use of fedratinib in this study or in other studies that is both serious and unexpected (ie, SUSAR);
- Any finding from tests in laboratory animals that suggests a significant risk for human subjects including reports of mutagenicity, teratogenicity, or carcinogenicity.

Where required by local legislation, the Investigator shall notify his/her IRB/EC promptly of these new serious and unexpected AE(s) or significant risks to subjects.

The Investigator must keep copies of all pertinent safety information on file including correspondence with Celgene and the IRB/EC. (See Section [14.3](#) for record retention information).

10.7. Adverse Events of Special Interest

An adverse event of special interest (AESI) is one of scientific and medical interest specific to understanding of the investigational product and may require close monitoring and rapid communication by the Investigator to the sponsor. All AESI (serious and non-serious) are to be recorded within the CRF and the data transmitted electronically to Celgene Drug Safety within 24 hours of the Investigator’s knowledge of the event. In the event electronic transmission is not available, a paper SAE Report Form will be completed and sent directly to Celgene Drug Safety,

ensuring the event is recorded on the CRF as well. The rapid reporting of AESIs allows ongoing surveillance of these events to characterize and understand them in association with the use of this investigational product. Events of special interest may be referred to external experts for review as needed.

10.7.1. Fedratinib AESI

The following are considered to be Adverse Events of Special Interest (AESIs) for Fedratinib:

- Encephalopathy, including Wernicke's or suspected cases of WE associated with thiamine levels below normal range.
- Thiamine levels below normal range with or without signs or symptoms of WE
- New malignancy after start of study treatment
- Progression of myelofibrosis to acute myeloid leukemia (AML)
- Cardiac failure or cardiomyopathy
- Grade 3 or 4 hyperlipasemia, or Grade 3 or 4 hyperamylasemia; according to CTCAE criteria, v 5.0 or events of pancreatitis
- Grade 3 or 4 alanine transaminase (ALT), aspartate transaminase (AST), or total bilirubin elevation or events of hepatotoxicity

11. DISCONTINUATIONS

11.1. Study Treatment Discontinuation

The following events are considered sufficient reasons for discontinuing a subject from fedratinib

- Lack of Efficacy
- Adverse Event
- Progression of Disease according to the IWG-MRT 2013 criteria
- Withdrawal by subject
- Death
- Lost to follow-up
- Pregnancy
- Protocol deviation
- Study terminated by Sponsor
- Treatment discontinuation guidance related to the Dose Modification Schedule table ([Table 4](#))
- Other (to be specified on the CRF)

The reason for discontinuation of treatment should be recorded in the CRF and in the source documents.

The decision to discontinue a subject from treatment remains the responsibility of the treating physician, which will not be delayed or refused by the Sponsor. However, prior to discontinuing a subject, the Investigator may contact the Medical Monitor and forward appropriate supporting documents for review and discussion.

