1.1.4. Medical Need

MPN-associated myelofibrosis, particularly intermediate or high-risk disease, is a serious and fatal condition. Until recently, ruxolitinib, a JAK1/2 inhibitor, was the only drug approved for the treatment of patients with intermediate or high-risk MF in the US. While the benefits of ruxolitinib therapy in terms of spleen response and improvement of constitutional symptoms are significant, ruxolitinib is also associated with the risks of treatment-associated anemia (40.4% vs 12.3% for BAT) and thrombocytopenia (44.5% vs 9.65% for BAT) (Harrison, 2012). The 1-, 2-, and 3-year discontinuation rates are 49, 71 and 86%, respectively. Major reasons for ruxolitinib treatment discontinuation are loss of therapeutic effect, lack of response and drug-induced cytopenias [REDACTED]. Additionally, responses to ruxolitinib are typically observed within the first 3–6 months after therapy initiation (Harrison, 2012; Verstovsek, 2012) and it has been suggested that for patients who have not had a reduction in spleen size or improvement in symptoms after that period, alternative therapies should be considered (Harrison, 2018; Keohane, 2013). The effect of ruxolitinib on overall survival (OS) continues to be debated and the unclear limited effects on bone marrow fibrosis and driver mutation allele burden suggest that the disease-modifying activity of the drug is likely to be minor.

Therefore, the unmet medical need for frontline MF patients remains high, despite the availability of ruxolitinib, especially for patients who have low baseline platelet counts and are susceptible to myelosuppression/thrombocytopenia.

¹ Jakafi is a registered trademark of Incyte Corporation.

² Jakavi is a registered trademark of Novartis AG in countries outside of the US.

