9.3. Sample Size Consideration

Assuming the primary endpoint response rate is 35%, 100 evaluable subjects will approximately yield 90% power to detect the lower bound of 95% confidence interval (calculated by Pearson-Klopper method) for primary endpoint response rate excludes 20%.

The study will enroll approximately 110 subjects by accounting for a 10% drop-out rate.

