9.6.4. Durability of Spleen Volume Response by MRI/CT (DR)

Durability of spleen volume response (DR) by MRI/CT is defined as time from the first documented spleen response (ie, $\geq 35\%$ reduction in spleen volume) to the date of subsequent progressive disease (PD) (ie, $\geq 25\%$ increase in spleen volume from baseline) or death, whichever is earlier. In the absence an event (ie, subsequent spleen volume reduction $< 35\%$ before the analysis is performed), the DR will be censored at the date of the last valid assessment performed before the analysis performed date.

Durability of spleen volume response by MRI/CT scan will be analyzed using Kaplan-Meier method. The K-M estimates of the 25th, 50th, and 75th percentiles and the 95% confidence interval of median will be provided, and the K-M curves will be plotted.

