9.6.5. Durability of Spleen Response by Palpation (DRP)

Durability of spleen response by palpation (DRP) is defined as time from the date of first documented palpable spleen response, according to the IWG-MRT 2013 (Appendix D) to the date of subsequent PD according to the IWG-MRT 2013 or death, whichever is earlier.

Durability of spleen response by palpation according to the IWG-MRT 2013 criteria will be calculated for subjects that have an enlarged spleen at baseline (≥ 5 cm below LCM), and that have a spleen response by palpation. In the absence of an event (ie, no loss of spleen response by palpation) before the analysis is performed, the DRP will be censored at the date of the last valid assessment performed before the analysis performed date.

Durability of spleen response by palpation will be analyzed using Kaplan-Meier (K-M) method. The K-M estimates of the 25th, 50th, and 75th percentiles and the 95% confidence interval of median will be provided, and K-M curves will be plotted.

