PR	Peripheral blood: Hemoglobin \geq 100 g/L and $<$ UNL; neutrophil count \geq 1 \times 10 ⁹ /L and $<$ UNL; platelet count \geq 100 \times 10 ⁹ /L and $<$ UNL; < 2% immature myeloid cells [‡] and Clinical: Resolution of disease symptoms; spleen and liver not palpable; no evidence of EMH or Bone marrow: [*] Age-adjusted normocellularity; < 5% blasts; \leq grade 1 MF [†] , and peripheral blood: Hemoglobin \geq 85 but $<$ 100 g/L and $<$ UNL; neutrophil count \geq 1 \times 10 ⁹ /L and $<$ UNL; platelet count \geq 50, but $<$ 100 \times 10 ⁹ /L and $<$ UNL; < 2% immature myeloid cells [‡] and Clinical: Resolution of disease symptoms; spleen and liver not palpable; no evidence of EMH
Clinical improvement (CI)	The achievement of anemia, spleen or symptoms response without progressive disease or increase in severity of anemia, thrombocytopenia, or neutropenia [§]
Anemia response	Transfusion-independent patients: a \geq 20 g/L increase in hemoglobin level Transfusion-dependent patients: becoming transfusion-independent {
Spleen response	A baseline splenomegaly that is palpable at 5-10 cm, below the LCM, becomes not palpable** or A baseline splenomegaly that is palpable at $>$ 10 cm, below the LCM, decreases by \geq 50%** A baseline splenomegaly that is palpable at $<$ 5 cm, below the LCM, is not eligible for spleen response A spleen response requires confirmation by MRI or computed tomography showing \geq 35% spleen volume reduction
Symptoms response[#]	A \geq 50% reduction in the MPN-SAF TSS ^{††}
Progressive disease^{‡‡}	Appearance of a new splenomegaly that is palpable at least 5 cm below the LCM or A \geq 100% increase in palpable distance, below LCM, for baseline splenomegaly of 5-10 cm or A 50% increase in palpable distance, below LCM, for baseline splenomegaly of $>$ 10 cm or Leukemic transformation confirmed by a bone marrow blast count of \geq 20% or A peripheral blood blast content of \geq 20% associated with an absolute blast count of \geq 1 \times 10 ⁹ /L that lasts for at least 2 weeks
Stable disease	Belonging to none of the above listed response categories
Relapse	No longer meeting criteria for at least CI after achieving CR, PR, or CI, or Loss of anemia response persisting for at least 1 month or Loss of spleen response persisting for at least 1 month

EMH, extramedullary hematopoiesis (no evidence of EMH implies the absence of pathology- or imaging study-proven non-hepatosplenic EMH); LCM, left costal margin; UNL, upper normal limit.

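### Section 9.6.4 gives two conflicting events for spleen volume durability; on the progression wording, leukemic transformation and stops for lack of efficacy are not events and durability can look too long

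*Combined protocol and SAP*

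**What the plan says.** Section 9.6.4 starts DR at the first documented reduction of at least 35%. It ends DR at progression, spelled out as a rise of at least 25%: "increase in spleen volume from baseline) or death, whichever is earlier". The next sentence, on censoring, describes the event differently, as a reduction that has dropped below 35%. Subjects without an event are censored at their last valid assessment. Table 2 describes DR as the duration of a reduction of at least 35% and closes its timeframe at the End of Treatment (EOT) visit.

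Section 9.6.5 ends DRP at the "date of subsequent PD according to the IWG-MRT 2013 or death, whichever is earlier". Its censoring sentence also describes the event as loss of response. Appendix D lists, as one form of progressive disease, "Leukemic transformation confirmed by a bone marrow blast count of" 20% or more. Its footnote requires splenic progression to be confirmed by a spleen volume increase of at least 25% from pretreatment baseline.

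Section 11.1 lists, as separate sufficient reasons for stopping fedratinib, "Lack of Efficacy" and "Progression of Disease according to the IWG-MRT 2013 criteria". Table 3 schedules MRI/CT up to EOT and none afterwards, although an unscheduled scan is allowed if splenic progression is suspected. Survival and progression to AML are followed for up to 12 months after EOT.

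**The concern.** The two descriptions in Section 9.6.4 are different endpoints: one measures time to volume progression, the other time to loss of response. An analyst cannot apply both.

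On the progression wording, two kinds of treatment failure have no DR event of their own. The first is leukemic transformation, which is an event for DRP, so the same occurrence has a different status in two sibling endpoints and no reason is given. The second is a stop for lack of efficacy when the spleen has regrown but not to 25% above baseline. Such a subject, if alive, has no further scheduled scan and is censored. Kaplan-Meier treats censored subjects as having the same future risk as those still followed. That is hard to believe for someone taken off the drug because it stopped working.

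Durability is a named secondary objective, and its main result is a Kaplan-Meier curve with its percentiles. The stake is a durability figure that is unclear in meaning and probably too long.

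**Working it through.** **The plan's own figures.** The documents give no expected value for DR, so there is none to reproduce. The sample size belongs to the primary endpoint: "Assuming the primary endpoint response rate is 35%, 100 evaluable subjects will approximately yield 90% power". With an exact 95% interval, 29 of 100 is the smallest count whose lower bound exceeds 20% (20.36%; 28 gives 19.48%). Power at 35% is then 0.915. That agrees with the plan and does not depend on the durability definition.

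**How far a responder must regrow.** Volumes are fractions of baseline. A responder has at most 0.65; the progression event needs at least 1.25; loss of response needs more than 0.65.

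- Response at exactly -35%: progression needs 1.25/0.65 = 1.92-fold growth; loss of response needs any growth above 0.65/0.65 = 1.00-fold.
- Response at -50%: progression needs 1.25/0.50 = 2.5-fold growth; loss of response needs growth above 0.65/0.50 = 1.30-fold.

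A spleen back at its baseline size (1.00) has lost its response but has not progressed. By palpation the gap is similar: Appendix D requires a doubling for a baseline of 5-10 cm, so a spleen of 8 cm that became non-palpable must reach 16 cm, with imaging confirmation.

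**Who has an event under each wording of 9.6.4.**

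| Responder's course | DR, progression wording | DR, below-35% wording | DRP, progression wording |
|---|---|---|---|
| Volume at least 25% above baseline | event | event | event if palpation criteria are also met |
| Leukemic transformation, alive, volume still reduced by 35% or more | censored | censored | event |
| Regrown to baseline, stopped for lack of efficacy, seen on EOT scan | censored | event | censored |
| Death | event (after EOT unclear, given Table 2) | not stated in that sentence | event |

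**Illustrative size.** Inputs: an all-failure median m = 10.4 months, borrowed from the duration of response that Section 1.2 quotes for the earlier Phase 3 study; and f, the share of response endings that DR does not count when they happen. The documents do not give f. Section 1.1.4 says "Major reasons for ruxolitinib treatment discontinuation are loss of therapeutic effect, lack of response and drug-induced cytopenias", which makes such stops plausible but concerns another drug and supplies no share.

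- If these endings are censored and never counted, constant independent hazards give a reported median of m/(1-f): 10.4/0.9 = 11.6, 10.4/0.8 = 13.0 and 10.4/0.7 = 14.9 months for f = 10, 20 and 30%. A simulation of 400,000 subjects gave 11.55, 13.05 and 14.88.
- If they are counted later at death (assumed median 3 to 6 months after failure, deaths within 12 months captured), the same simulation gave 10.9-11.1, 11.3-11.8 and 11.8-12.6 months.
- If all are counted at failure, the median returns to 10.4.

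**The case against.** The case for leaving the plan alone has several parts, and some of it stands.

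- *A reader might infer that DR has no event for IWG-MRT progression at all.* The documents do not support this. The volume increase that Appendix D requires to confirm splenic progression is the DR event itself. Only the leukemic and blast part is missing.
- *A reader might infer that every responder who stops for lack of efficacy is certain to be censored.* That ignores the censoring sentence. If a reduction below 35% is the event, regrowth seen on the EOT scan counts. The summary of changes to Section 9.6.4 says durability was moved from loss of response to progression or death, which suggests the sentence is a remnant, but the current text still contains both. Even on the below-35% reading, transformation with a still-reduced spleen is not counted.
- *A reader might infer that Section 11.1 forces these stops.* It lists sufficient reasons and leaves the decision to the treating physician. The argument needs only that such stops occur.
- *Death is an event.* This stands and reduces the distortion. It does not remove it, because the event comes late and the EOT timeframe in Table 2 leaves later deaths in doubt.
- *The m/(1-f) figures are not a measured bias.* This also stands. Under independent hazards, censoring is non-informative and Kaplan-Meier is correct for its own target. The figures show the gap between two endpoint definitions. The anchor comes from previously untreated patients pooled over two doses, and the documents do not say which events ended response there.
- *Progression may have been chosen on purpose, and Section 9.1 defers details to a separate SAP.* Both are possible. The documents reviewed do not state a spleen-only target or explain why DR and DRP differ, and the conflict inside Section 9.6.4 must be settled in any case.

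**Conclusion.** The point holds in a limited form. Section 9.6.4 contains two incompatible DR events. On the progression wording, which the amendment summary indicates is intended, leukemic transformation counts for DRP but not for DR. A living responder who stops for lack of efficacy below +25% is censored at the last valid assessment. That censoring is likely informative, and the effect is towards longer reported durability.

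The size is unknown. For f = 10-30% and an illustrative 10.4-month median, the reported median would be about 10.9-12.6 months if later deaths count and 11.6-14.9 if they do not. These ranges rest on constant independent hazards, an assumed f, an assumed time from failure to death and a borrowed anchor. They show the order of the effect and are not a forecast. DR is a secondary, descriptive endpoint; the primary endpoint and sample size are unaffected. This is a cheap improvement that should be made, not an obstacle to the trial.

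**What to change.** 1. In Section 9.6.4, keep one DR event definition, and correct the censoring sentences in 9.6.4 and 9.6.5 to match their events. Bring the Table 2 description into line.
2. Use the same progression definition for DR as for DRP by adding leukemic transformation, dated at confirmation. State whether deaths after EOT count, given the timeframe in Table 2.
3. Prespecify one sensitivity analysis for DR and DRP in which documented loss of response (for DR, a reduction below 35%) and stops coded "Lack of Efficacy" are events. Tabulate censored responders by reason for discontinuation.

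The cost is wording, one extra Kaplan-Meier analysis per endpoint and one table. Stop reasons and AML status are already recorded on the CRF, so no new procedure is needed. There are two downsides. Lack of efficacy is an open-label investigator judgement, which is why it belongs in the sensitivity analysis only. The durability figure will also become less favourable.
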